### 1.3.2 Part B

Procedure b	Intervention period (Part B) a												Last follow-up visit c	Early IMP discontinuation visit e
	Week 28 (Day 197±3)	Week 30 (Day 211±3)	Week 32 (Day 225±3)	Week 34 (Day 239±3)	Week 36 (Day 253±3)	Week 40 (Day 281±3)	Week 44 (Day 309±3)	Week 52 (Day 365±3)	Week 64 (Day 449±3)	Week 76 (Day 533 ±3)	Week 88 (Day 617 ±7)	Week 104 (Day 729 ±7)		
Visit	10	10.25	10.5	10.75	11	11.5	12	13	14	15	16	17	18	
Visit location or medium	Site	Site d	Site d	Site d	Site	Site d	Site	Site	Site	Site	Site	Site	Site	Site
Study intervention dispensing and reconciliation f	X				X		X	X	X	X	X	X g		X g
Physical examination h	X				X		X	X	X	X	X	X	X	X
Neurological examination i	X				X		X	X	X	X	X	X	X	X
Laboratory tests for hematology and chemistry	X	X j	X j	X j	X	X j	X	X	X	X	X	X	X	X
12-lead ECG	X				X			X		X		X	X	X
C-SSRS questionnaire k	X				X		X	X	X	X	X	X	X	X
Vital signs l	X				X		X	X	X	X	X	X	X	X
Weight	X				X		X	X	X	X	X	X	X	X
SVC	X				X		X	X	X	X	X	X		X
ALSFRS-R	X				X		X	X	X	X	X	X		X
ALSAQ-5	X				X		X	X	X	X	X	X		X
Blood sample for plasma PK	X m													

Abbreviations: AE = adverse event; ALSAQ-5 = Amyotrophic Lateral Sclerosis Assessment Questionnaire-5; ALSFRS-R = Amyotrophic Lateral Sclerosis Functional Rating Scale – Revised;  $\beta$ -HCG = beta human chorionic gonadotropin; C-SSRS = Columbia Suicide Severity Rating Scale; DTP = direct-to-patient; ECG = electrocardiogram; [REDACTED];

IMP = investigational medicinal product; Nfl = neurofilament light; PK = pharmacokinetic(s); SAE = serious adverse event; SVC = slow vital capacity; WOCBP = woman of childbearing potential

a An urgent safety measure was submitted on 05 December 2023 to request pause of SAR443820 administration in Part B (open-label extension) immediately. All participants in Part B will be encouraged to continue follow-up visits, but no doses of SAR443820 should be administered until DMC recommendation to resume dosing based on benefit-risk considerations when Part A data is available.

b The first visit for Part B is the Week 24 Visit in Part A

- b The first visit for Part B is the Week 24 visit in Part A.
- c The last follow-up visit will happen 2 weeks ( $\pm 3$  days) after Week 104 visit (Visit 17).

- d* Alternatively, the Week 30, Week 32, Week 34 and Week 40 visit can be conducted by phone. The blood sample at these visits must be collected either at study site, at a local clinic or at home by a nurse. In case of testing at a local lab, the study site staff must contact the participant, within 2 working days after the results are expected to be available, to collect results of blood test and update them in the eCRF. When Week 32 and Week 40 visits are conducted by phone, the urine pregnancy test will be provided directly to participants and self-conducted at home. The study site staff will call the participants to remind them to conduct the pregnancy test and collect the result. If pregnancy test result is positive, participant should discontinue IMP immediately.
- e* For participants who prematurely discontinue IMP, the early IMP discontinuation visit will happen 2 weeks ( $\pm 3$  days) after the last dose of the IMP. If, after the IMP discontinuation visit, participants decide to continue the study, they will follow the same schedule for visits, but only ALSFRS-R, blood sample for NfL, vital signs, physical examination, neurological examination, AE review, SAE review and concomitant therapy and procedures recordings will be performed in the visits, as applicable according to the schedule of activities.
- f* In addition to the IMP being dispensed in the clinic, the IMP may be dispensed for home administration via DTP services, except if prohibited by local regulatory authorities.
- g* Only IMP reconciliation will be done at this visit.
- h* A brief physical examination will be performed at each visit. The skin and lymph nodes need to be checked at each visit.
- i* A brief neurological examination pertaining to cranial nerves, coordination/cerebellar function, reflexes, and motor function will be performed at each visit.
- j* Only liver chemistry monitoring will be conducted, which includes testing of alanine transaminase (ALT), aspartate aminotransferase (AST), bilirubin direct, bilirubin total and alkaline phosphatase.
- k* The "Since Last Visit" version of the C-SSRS will be used.
- l* Vital signs include blood pressure, heart rate, respiratory rate, weight, and temperature.
- m* One sample for PK will be collected within 1 hour before the morning dose of IMP. This PK sample can be taken under either fasting or non-fasting condition.
- n* The blood sample for serum NfL will be collected only when the participant terminates IMP before Week 52.
- o* Monthly urine pregnancy tests will be provided directly to participants and self-conducted by them at home when not coinciding with a clinic visit. The study site staff will call the participants to remind them to conduct the monthly pregnancy tests and collect the results. If pregnancy test result is positive, participant should discontinue IMP immediately.

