## 1.3 SCHEDULE OF ACTIVITIES

### 1.3.1 Part A

Procedure	Screening (up to 4 weeks before Day 1)	Intervention period (Part A)													Early IMP discon- tinuation visit b	
		Day 1		Week 2 (Day 15±3)	Week 4 (Day 29±3)	Week 6 (Day 43±3)	Week 8 (Day 57±3)	Week 10 (Day 71±3)	Week 12 (Day 85±3)	Week 16 (Day 113±3)	Week 20 (Day 141±3)	Week 21 (Day 148±3)	Week 22 (Day 155±3)	Week 23 (Day 162±3)	Week 24 (Day 169±3) a	
		Predose (baseline)	Postdose													
Visit	1 c	2		3	4	4.5	5	5.5	6	7	8	8.25	8.5	8.75	9	
Visit location or medium	Site	Site		Site	Site	Site d	Site	Site d	Site d	Site	Site d	Site d	Site d	Site d	Site	Site
Informed consent	X															
Eligibility check (inclusion and exclusion criteria)	X	X														
Demography	X															
Randomization		X e														
Study intervention dispensing and reconciliation f		X		X g	X		X			X					X h	X g
Physical examination i	X	X		X	X		X			X					X	X
Height	X															
Weight	X	X		X	X		X			X					X	X
12-lead ECG	X	X		X			X								X	X
Vital signs j	X	X	X k	X	X		X			X					X	X

Procedure	Screening (up to 4 weeks before Day 1)	Intervention period (Part A)													Early IMP discon- tinuation visit b	
		Day 1		Week 2 (Day 15±3)	Week 4 (Day 29±3)	Week 6 (Day 43±3)	Week 8 (Day 57±3)	Week 10 (Day 71±3)	Week 12 (Day 85±3)	Week 16 (Day 113±3)	Week 20 (Day 141±3)	Week 21 (Day 148±3)	Week 22 (Day 155±3)	Week 23 (Day 162±3)	Week 24 (Day 169±3) a	
		Predose (baseline)	Postdose													
Visit	1 c	2		3	4	4.5	5	5.5	6	7	8	8.25	8.5	8.75	9	
Visit location or medium	Site	Site		Site	Site	Site d	Site	Site d	Site d	Site	Site d	Site d	Site d	Site d	Site	Site
C-SSRS questionnaire	X	X l		X l	X l		X l			X l					X l	X l
Neurological examination m	X	X		X	X		X			X					X	X
Past and current medical conditions (includes substance usage) n	X	X														
Serum β-HCG test (WOCBP only)	X															X
Serum FSH and estradiol o	X															
Urine pregnancy test (WOCBP only)		X		X	X		X		X	X	X				X	
HIV and hepatitis B and C screening	X															

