		Day 1		Week 2 (Day 15±3)	Week 4 (Day 29±3)	Week 6 (Day 43±3)	Week 8 (Day 57±3)	Week 10 (Day 71±3)	Week 12 (Day 85±3)	Week 16 (Day 113±3)	Week 20 (Day 141±3)	Week 21 (Day 148±3)	Week 22 (Day 155±3)	Week 23 (Day 162±3)	Week 24 (Day 169±3) a	
		Predose (baseline)	Postdose													
Visit	1 c	2		3	4	4.5	5	5.5	6	7	8	8.25	8.5	8.75	9	
Visit location or medium	Site	Site		Site	Site	Site d	Site	Site d	Site d	Site	Site d	Site d	Site d	Site d	Site	Site
Concomitant therapy and procedures recording		←-----→														X

Abbreviations: AE = adverse event; ALS = amyotrophic lateral sclerosis; ALSAQ-5 = Amyotrophic Lateral Sclerosis Assessment Questionnaire – 5; ALSFRS-R = Amyotrophic Lateral Sclerosis Functional Rating Scale – Revised; β-HCG = beta human chorionic gonadotropin; CHI3L1 = chitinase-3-like protein 1; C-SSRS = Columbia Suicide Severity Rating Scale; DTP = direct-to-patient; ECG = electrocardiogram; [REDACTED]; FSH = follicle stimulating hormone; [REDACTED] HIV = human immunodeficiency virus; IFNy = interferon γ; IL = interleukin; IMP = investigational medicinal product; IP-10 = interferon gamma-induced protein 10; MCP = monocyte chemoattractant protein; MIP1 = macrophage inflammatory protein-1; NfL = neurofilament light chain; p75ECD = extracellular domain of p75; PK = pharmacokinetic(s); SAE = serious adverse event; sTREM2 = soluble triggering receptor expressed on myeloid cells 2; SVC = slow vital capacity; TARC = thymus- and activation-regulated chemokine; TNF = tumor necrosis factor; WOCBP = woman of childbearing potential

- a The Week 24 visit is considered as both the last visit for Part A and the first visit for Part B. For all participants, last dose of double-blind IMP should be taken on the day prior to the Week 24 visit. Week 24 visit will consist of first open-label (Part B) IMP. All assessments for end of Part A should be completed prior to first dose of open-label IMP.

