- b For participants who prematurely discontinue IMP, the early discontinuation visit will happen 2 weeks (±3 days) after the last dose of the IMP. If, after the early IMP discontinuation visit, participants decide to continue the study, they will follow the same schedule for visits, but only ALSFRS-R, SVC, blood samples for plasma sTREM2, blood samples for serum biomarkers, including NfL, CHI3L1, cytokine and chemokine panel and urine sample for biomarker analysis (p75ECD), vital signs, physical examination, neurological examination, AE review, SAE review and concomitant therapy and procedures recordings will be performed in the visits, as applicable according to the schedule of activities.
- c The screening visit can be performed over up to 2 days if needed (they do not need to be consecutive days) to minimize the burden on participants.
- d Alternatively, the Week 6, Week 10, Week 12, Week 20, Week 21, Week 22, and Week 23 visit can be conducted by phone. If the study visit is conducted by phone, the blood sample must be collected at a local clinic or at home by a nurse, and the sample must be tested at a local lab or the central lab. In case of testing at a local lab, the study site staff must contact participants, within 2 working days after the results are expected to be available, to collect results of blood test.; For Week 12, and Week 20 visit, if conducted by phone, 1) the urine pregnancy test will be provided directly to participants and self-conducted at home. The study site staff will call the participants to remind them to conduct the pregnancy test and collect the result. If pregnancy test result is positive, participant should discontinue IMP immediately; 2) ALSFRS-R will be measured through the phone call.
- e Participants will be randomized in a 2:1 ratio to the SAR443820 treatment arm or placebo arm. The randomization will be stratified by the geographic region of the study site, region of ALS onset (bulbar vs other areas), use of riluzole (yes vs no), and use of edaravone (yes vs no) and use of the combination of sodium phenylbutyrate and taurursodiol (yes vs no).
- f In addition to the IMP being dispensed in the clinic, the IMP may be dispensed for home administration via DTP services, except if prohibited by local regulatory authorities.
- g Only IMP reconciliation will be done at this visit.

- h* Reconciliation of the IMP dispensed in Part A and dispensation of the open-label IMP in Part B at this visit (Week 24).

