## **7.1.2 Temporary discontinuation**

Temporary intervention discontinuation may be considered by the Investigator because of suspected AEs or disruption of the clinical trial due to a regional or national emergency declared by a governmental agency (Appendix 9 [[Section 10.9](#)]). For all temporary intervention discontinuations, duration should be recorded by the Investigator in the appropriate pages of eCRF. Temporary discontinuation of study intervention is defined as stopping study intervention for a minimum of 1 day and a maximum of 2 weeks accumulative in Part A or 8 weeks accumulative in Part B.

Based on a data review and in accordance with DMC recommendations, the sites were instructed on 5th December 2023 to pause administration of SAR443820 in Part B (open-label extension) immediately. An early IMP discontinuation visit should happen 2 weeks after the last dose of IMP. All participants in Part B will be encouraged to continue follow-up visits, but no doses of SAR443820 should be administered. Participants who are in Part A, rollover to Part B for follow-up visits after completing Part A is encouraged, but without taking SAR443820 in Part B. An early IMP discontinuation visit should also happen 2 weeks after the last dose of IMP. The decision of whether resuming SAR443820 administration in Part B will be made based on DMC recommendation when Part A data is available and benefit risk ratio will be evaluated.

If a scheduled liver chemistry monitoring is missed during weekly assessments, an unscheduled assessment for liver chemistry monitoring should be completed within 3 days. If a participant is receiving IMP and is unable to comply with the monitoring schedule, but does not meet the permanent discontinuation criteria, the participant must stop IMP administration until liver chemistry monitoring can be completed.

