#### **8.2.6 Pregnancy testing**

For female participants of childbearing potential, a pregnancy test will be performed at each onsite visit during the whole study period. Additionally, monthly urine pregnancy tests will be provided directly to participants and self-conducted by them at home when not coinciding with a clinic visit. The study site staff will call the participants to remind them to conduct the monthly pregnancy tests and collect the results. A serum pregnancy test will be conducted at the screening visit, the last follow-up visit at Week 106, and the early discontinuation visit, and a urine pregnancy test will be performed for all other visits.

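### The schedule footnotes for visits after stopping drug omit the pregnancy test that Section 8.2.6 requires, leaving the test unclear between about day 14 and day 32 after the last dose

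*Protocol*

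**What the plan says.** **Visits after stopping drug.** In Protocol 1.3.1, footnote b, "the early discontinuation visit will happen 2 weeks (±3 days) after the last dose of the IMP". Participants who then stay in the study keep the visit schedule with a reduced set of procedures. The list opens with the ALSFRS-R, SVC and biomarker samples, and ends: "vital signs, physical examination, neurological examination, AE review, SAE review and concomitant therapy and procedures recordings will be performed in the visits". In Protocol 1.3.2, footnote e gives the Part B list: "only ALSFRS-R, blood sample for NfL, vital signs, physical examination, neurological examination, AE review, SAE review and concomitant therapy and procedures recordings". Neither list includes a pregnancy test.

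**Pregnancy testing.** Protocol 8.2.6 states: "For female participants of childbearing potential, a pregnancy test will be performed at each onsite visit during the whole study period". It specifies a serum test at screening, at the early discontinuation visit and at the Week 106 follow-up, and a urine test at all other visits. Between clinic visits there are home tests, which Part B footnote o describes as follows: "Monthly urine pregnancy tests will be provided directly to participants and self-conducted by them at home when not coinciding with a clinic visit". Protocol 2.3.1, Table 2, names monthly testing of all women of childbearing potential as part of the mitigation for embryo-fetal risk. Protocol 5.1 (I 10 b) requires contraception for at least 32 days after the last dose.

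**The Part B pause.** Protocol 7.1.2 stops dosing in Part B from 5 December 2023 and encourages participants to keep attending. For those rolling over from Part A without drug it adds: "An early IMP discontinuation visit should also happen 2 weeks after the last dose of IMP".

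**The concern.** A site cannot both limit a visit to a closed list without a pregnancy test and test at each onsite visit. Protocol Section 8 treats adherence to the schedule as required and allows no waivers, so the choice is not left to the site. The closing words of the footnotes, which refer back to the schedule of activities, govern when the listed items are done. They do not add items.

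The home tests do not settle the matter. They are worded for months in which no clinic visit coincides. If a test falls due at a clinic visit, the home-test rule points to the clinic and the footnote leaves the test out.

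At stake is uniform detection of pregnancy inside the sponsor's own 32-day precaution period. Embryo-fetal toxicity is a listed potential risk. Pregnancy is an adverse event of special interest with 24-hour notification (Protocol 8.3.8), and the SAP selects it from a dedicated CRF page (SAP 3.6.2, Table 6).

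**Working it through.** The plan states no figure on this point, so the check is a comparison of texts plus day arithmetic. All counts below are calendar days, not participants.

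**Inputs**
- Early discontinuation visit: day 14 ± 3 after the last dose (1.3.1 footnote b, 1.3.2 footnote e).
- Contraception period for women: at least 32 days (5.1).
- Part A urine tests after Day 1: Weeks 2, 4, 8, 12, 16, 20 and 24. Week 20 is Day 141 and Week 24 is Day 169 (1.3.1).
- Week 28: site visit, Day 197 ± 3 (1.3.2).
- Last Part A dose before rollover: "last dose of double-blind IMP should be taken on the day prior to the Week 24 visit", so nominally Day 169 − 1 = 168.
- All participants had passed Week 19 by 5 December 2023. Amendment 05, which set the current footnote text, is dated 13 December 2023 (amendment summary).

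**1. Length of the uncertain stretch.** The serum test at the early discontinuation visit falls on day 11 to 17.
- Nominal: 32 − 14 = 18 days remain.
- Range: 32 − 17 = 15 to 32 − 11 = 21 days.

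**2. Reach in Part A.** Week 19 is Day 141 − 7 = 134. Anyone at Day 134 or later on 5 December was at Day 142 or later on 13 December (134 + 8). The Week 8, 12 and 16 tests were therefore past for everyone. The nominal Week 20 day (141) was also past, and only a visit late in its window (up to Day 144) could remain. That leaves the Week 24 test. It falls after the discontinuation visit and inside the 32 days when last-dose day d satisfies d + 14 < 169 ≤ d + 32:
- d = 137 to 154, which is 18 possible last-dose days.
- With the discontinuation visit at day 17: d = 137 to 151, 15 days.
- With it at day 11: d = 137 to 157, 21 days.

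**3. Rollovers without drug.** The nominal last dose is Day 168 and the 32 days end on Day 168 + 32 = 200.
- Week 28 nominal: 197 − 168 = 29 days after the last dose.
- Week 24 on its nominal day, Week 28 anywhere in its window: 194 − 168 = 26 to 200 − 168 = 32 days.
- Both windows free: 194 − 171 = 23 to 200 − 165 = 35 days.

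So the Week 28 visit usually falls inside the contraception period and after the serum test. Section 8.2.6 calls for a urine test there, and footnote e omits it.

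**4. Participants already in Part B at the pause.** With a last dose on 5 December 2023, day 14 is 19 December 2023 and day 32 is 6 January 2024. Only visits between those dates fall in the uncertain stretch.

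**The case against.** The strongest reply is that the reduced lists were deliberate. The Amendment 05 summary says they simplify follow-up for people no longer taking drug. The serum test at about day 14 is kept. The footnotes govern what is done at visits, so they do not cancel monthly home testing, and Table 2 asks for that testing with no off-drug exception. Section 8.2.6 may not be meant literally either: the Part A schedule marks no urine test at Weeks 6, 10, 21, 22 or 23, although these can be site visits.

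Much of this stands. A reader might infer that women off drug go untested, and the documents do not support that: the serum test and the home tests both remain. A reader might also apply the Part A calculation to every possible stopping day and conclude that many early stops lose a scheduled test. That does not hold either, because participants were already beyond those visits when the current footnote text was issued.

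What does not fall away is the contradiction at visits where a test is otherwise due. Week 24 carries one in the Part A schedule, and Week 28 is an onsite visit under 8.2.6. Section 8.2.6 was not given an exception to match the simplification. Reading the home-test rule generously may be what was intended, but the text does not say so.

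**Conclusion.** The conflict between footnotes b and e and Section 8.2.6 is confirmed. It is minor. It affects the in-visit test over the last 15 to 21 days of a 32-day period, for late Part A stops and for participants taken off drug by the pause. The number of women concerned cannot be computed from the documents. It is likely to be small, and contraception is required throughout.

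Efficacy analyses are unaffected. The treatment-emergent period ends no later than 14 days after the last dose (SAP 3.1), so an event first dated after that would appear only in the special-interest listing or post-treatment summaries.

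Two assumptions carry the Part B reach. First, footnote e is taken to govern paused participants, because 7.1.2 gives them the early discontinuation visit that triggers it. Second, Section 8.2.6 alone is taken to require the Week 28 test, because the Part B pregnancy-test row is not legible in the text available.

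A reader might also infer that the plan breaks its own rule for people who leave at the 2-week visit, since Section 8.3.5 collects pregnancies to the end of the contraception period (32 days for women, 92 days for male participants) and no contact is scheduled that late. The documents do not support calling this an error. Section 8.3.5 sets a collection window. Sections 8.3.1 and 8.3.5 put no duty on investigators to seek adverse-event or pregnancy-related serious-event information once participation has ended. Extra calls after exit would be a preference.

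**What to change.** - Add to the lists in footnotes b and e: urine pregnancy test (women of childbearing potential), at visits up to at least 32 days after the last dose of study drug.
- State in both places that monthly home tests continue until at least that day.
- Amend Section 8.2.6 to carry the same rule for participants off drug, so that the schedule and the text agree.

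Optionally, align Appendix 4, which speaks of pregnancies during study participation, with the longer window in Section 8.3.5. This is housekeeping.

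The cost is a few words plus a urine test at a visit the participant already attends. Ending the requirement at day 32 or shortly after keeps the simplification that Amendment 05 was aiming for.

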## 2 INTRODUCTION

SAR443820 is a novel, potent, selective, CNS-penetrant RIPK1 inhibitor that is being developed for neurodegenerative diseases, including ALS.

### 2.1 STUDY RATIONALE

SAR443820 is a selective, orally bioavailable, CNS-penetrant, RIPK1 inhibitor. The aim of this placebo-controlled Phase 2 study is to determine the efficacy, safety, tolerability, PK, and PD of SAR443820 in treating adult participants with ALS.

Multiple pathways have been suggested to be involved in ALS pathogenesis, including pathways involved in oxidative stress, mitochondrial dysfunction, axonal damage, excitotoxicity, neuroinflammation, and protein aggregation (1). Treatment targeting the common mediator of these mechanisms can provide a more robust disease intervention than targeting any individual pathway. More specifically, inhibition of microglial activation and inflammatory-driven neuronal death, the common consequence of multiple pathways in the pathophysiology of ALS, has the potential to provide an effective treatment for this relentless disease.

RIPK1 is an intracellular protein involved in the regulation of inflammation, cytokine release, and cell death. RIPK1 is activated in response to several inflammatory stimuli, most notably TNF- $\alpha$  signaling through its receptor 1 (TNF1), with subsequent RIPK1 initiation of a complex signaling cascade that triggers intracellular responses, including cytokine release, microglial activation, and necroptosis, a regulated form of cell death (2, 3). Inhibition of RIPK1 activity has been shown to protect against necroptotic cell death in vitro across a range of cell death models (4, 5, 6). Similarly, in various animal models of diseases ranging from AD to MS, inhibition of RIPK1 protects against their respective pathologies and attributed cell death (7, 8, 9, 10). These nonclinical findings, coupled with observations of increased RIPK1 activity in human diseases (6, 7, 11), suggest that inhibition of RIPK1 could ameliorate ALS.

The RIPK1 pathway is activated in spinal cords from patients with ALS. These postmortem samples show elevated levels of RIPK1 and its downstream signaling partners, RIPK3 and MLKL (8). Similar increases have been observed in the spinal cord of the SOD1 (G93A) transgenic mouse with ALS. Furthermore, both genetic inhibition of the RIPK1 pathway (RIPK3 -/-) and treatment with a RIPK1 inhibitor reduced axonal pathology and delayed the onset of motor dysfunction in this model (8). Several ALS-inducing mutations, including TBK1 and OPTN, have been shown to sensitize cells to RIPK1-dependent cell death and inflammation (8, 12, 13). Notably, another RIPK1 activity inhibitor, transforming growth factor  $\beta$ -activated kinase-1 (TAK1), declines with age, which might predispose the CNS to neuroinflammation and neurodegeneration in the setting of genetic or environmental stresses (13).

In summary, both preclinical and patient-derived data have suggested RIPK1 may be a key mediator of necroptosis and inflammatory pathways in ALS. SAR443820, a CNS-penetrant inhibitor of RIPK1, has the potential to modify the course of neurodegenerative processes and slow disease progression in patients with ALS. Therefore, the aim of this Phase 2 study is to assess the efficacy, safety, and tolerability of SAR443820 in treating participants with ALS.

